7.2.2 Handling of missing or incomplete dates

Imputation rules for missing or partial AE start date are defined below:

If the start date has month and year but day is missing, the first day of the month will be imputed

- [REDACTED]
- [REDACTED]
- [REDACTED]

If the start date has year, but day and month are missing, the 1st of January will be imputed

- [REDACTED]
- [REDACTED]
- [REDACTED]

If the start date of an event is completely missing, then it is imputed with the first dose date.

Imputation rules for missing or partial AE stop date are defined below:

- [REDACTED]
- [REDACTED]
- [REDACTED]
- [REDACTED]

After the imputation, the imputed dates will be compared against the date of death, if available. If the date is later than the date of death, the date of death will be used as the imputed date instead.

Imputation rules for missing or partial medication start/stop dates are defined below:

Missing or partial medication start date:

- [REDACTED]
- [REDACTED]

Missing or partial medication stop date:

- [REDACTED]
- [REDACTED]
- [REDACTED]

Statistical Analysis Plan (SAP)

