8.6.3 Analysis of secondary endpoints

All secondary analyses will be performed using the FAS, unless otherwise stated. The response-type endpoints [REDACTED] will be analyzed based on the methods described for ACR20 in primary analysis. Continuous endpoints [REDACTED]

will be analyzed based on an MMRM analysis that includes the fixed effects of treatment, visit, treatment by visit interaction, prior anti-TNF use [REDACTED] Baseline weight [REDACTED] and Baseline value. Due to [REDACTED] Tildrakizumab and placebo group switching [REDACTED] Tildrakizumab [REDACTED], the comparisons between active drug and placebo will not be

Statistical Analysis Plan (SAP)

performed for the secondary endpoints collected after [REDACTED]. Response-type and continuous endpoints after [REDACTED] will be summarized descriptively. In addition, proportion of subjects who require adjustment of background therapy at [REDACTED] be presented with descriptive statistics.

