8.7.1 Adverse events

All AEs will be classified by Primary System Organ Class (SOC) and Preferred Term (PT) according to the most recently available version of the MedDRA dictionary.

Statistical Analysis Plan (SAP)

In summaries by SOC and PT, adverse events will be sorted within each SOC and PT in alphabetical order. In summaries by PT, AEs will be sorted within each PT in alphabetical order.

Details for imputing missing or partial start dates of adverse events are described in [REDACTED].

TEAEs are defined as any AE occurring or worsening on or after the first dose of IMP. AE summary tables will be presented for TEAEs only and will include the following:

- All TEAEs
- Related TEAEs (AE will be defined as related if causality is possibly, probably, or certain)
- TEAEs by maximum severity
- TEAEs leading to discontinuation
- Serious TEAEs
- TEAEs leading to death.

An overall summary for the categories above will be prepared by study part, treatment group and overall. A TEAE in [REDACTED] is defined with the event start date on/after the [REDACTED] but before [REDACTED] date of IMP or on/before the last dose date of IMP if the subject discontinues treatment before [REDACTED]. A TEAE in [REDACTED] defined with the event start date on/after [REDACTED] dosing date but on/before the [REDACTED]. A TEAE in [REDACTED] is defined with the event start date after the last dose date of IMP.

In addition, all TEAEs will be summarized by study part [REDACTED] SOC, PT and treatment group using frequency counts and percentages (i.e., number and percentage of subjects with an event).

Where a subject has the same adverse event, based on preferred terminology, reported multiple times in a specific study part, the subject will only be counted once at the preferred terminology level in adverse event frequency tables.

Where a subject has multiple adverse events within the same system organ class in a specific study part, the subject will only be counted once at the system organ class level in adverse event frequency tables.

When reporting adverse events by intensity, in addition to providing a summary table based on the event selection criteria detailed above, summary table will also be provided based on the most intense event - independent of relationship to study treatment.

[REDACTED]

[REDACTED]

[REDACTED]

[REDACTED]

[REDACTED]

[REDACTED]

Statistical Analysis Plan (SAP)

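### Completely undated AEs are always given the first dose date, so placebo subjects who switch to tildrakizumab have them tabulated under placebo even when onset followed the switch (minor)

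*SAP*

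**What the plan says.** Four statements in the SAP bear on this.

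- **Imputation (section 7.2.2).** For an AE with no start date at all: "If the start date of an event is completely missing, then it is imputed with the first dose date". The rule carries no condition and no sub-bullets. The redacted start-date bullets sit under the two partial-date rules (day missing; day and month missing).
- **Check on the imputed date (section 7.2.2).** After imputation, "the imputed dates will be compared against the date of death, if available", and "If the date is later than the date of death, the date of death will be used as the imputed date instead". No other check is legible.
- **TEAE status and study part (section 8.7.1).** "TEAEs are defined as any AE occurring or worsening on or after the first dose of IMP". A TEAE in the first of three windows "is defined with the event start date on/after the" (redacted) and before a later IMP date, with a variant for subjects who discontinue earlier. The second window runs from a later dosing date. A TEAE in the third "is defined with the event start date after the last dose date of IMP". Results are split accordingly: "An overall summary for the categories above will be prepared by study part, treatment group and overall".
- **Change of treatment (sections 8.6.3 and 6.5).** Section 8.6.3 gives "Tildrakizumab and placebo group switching" to tildrakizumab as the reason for ending comparisons with placebo at a redacted time. Section 6.5 leaves out assay results from the placebo portion but admits subjects who are treated with tildrakizumab in Part 2.

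**The concern.** Giving an undated AE the first dose date is a cautious convention when each subject has one treatment throughout. It makes the event treatment-emergent, and there is only one treatment to attribute it to. Here the same date does a second job: it decides the study part, and for a placebo subject who switches it therefore decides the treatment. For that job the convention is not cautious. It can move an event that began on tildrakizumab back to placebo, but it can never do the reverse.

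The affected table is the one that matters most for safety, because the first part is the placebo-controlled one. Section 8.7 plans no safety tests, so the descriptive incidences by part and treatment group are the comparison. Events wrongly placed there raise the placebo incidence and are missing from the part after the switch.

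A second, narrower gap concerns AEs known to have ended before dosing. Section 8.7.1 confirms that pre-treatment AEs are recorded, so the case can arise. With no legible check against the stop date, such an AE without a start date would be moved to a start after its own end.

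**Working it through.** The plan gives no figure to reproduce, so the check is to apply the two rules in sequence.

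**Notation.** Day 1 is the first IMP dose, S the first dose after the switch, L the last dose and D the date of death, if any. The actual days are redacted, so all values of S and L below are assumptions. Two readings are also assumed: that the first dose date in 7.2.2 means the first IMP dose, as in the TEAE definition, and that the first window in 8.7.1 opens at that dose.

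**Step 1, impute.** Start = day 1.

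**Step 2, death check.** Start = min(1, D). A dosed subject cannot have died before day 1, so D ≥ 1 and the start stays at day 1. This check can only move a date earlier, never into a later part.

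**Step 3, allocate.**
- First part: 1 ≤ start < S. Day 1 always qualifies.
- Second part: S ≤ start ≤ L. Day 1 never qualifies, because S > 1.
- Third part: start > L. Day 1 never qualifies, because L ≥ 1.

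**Example.** Take S = 169 and L = 337. A placebo subject's AE begins on day 253, which is 253 − 169 = 84 days after the first tildrakizumab dose, but has no recorded start date. It is imputed to day 1. Since 1 < 169, it is tabulated in the first part, under placebo.

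**Enumeration.** The rules were run for S = 85, 113, 169 and 197, with L at S, S + 84 and S + 168, across true onset days, with and without a death date. Subjects who discontinued in the first part were run as well. Every undated AE went to the first part and none to a later one.

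**How often is that wrong?** Only when true onset was on or after S. If onset were spread evenly over the days from first to last dose, the share would be (L − S + 1) / L:

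| S | L | Share with onset at or after the switch |
|---|---|---|
| 169 | 253 | 85/253 = 34% |
| 169 | 337 | 169/337 = 50% |
| 85 | 337 | 253/337 = 75% |

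These are illustrations, not trial figures.

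**Number of events.** The rate of undated AEs is not given. Assume 100 AEs with true onset after the switch among placebo switchers, of which 1% to 3% have no start date. Then 100 × 0.01 = 1 to 100 × 0.03 = 3 events are tabulated under placebo instead of tildrakizumab.

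**Stop-date case.** Suppose an AE has a known stop date before day 1 and no start date. Step 1 gives start = day 1, which is later than the stop. Step 2 does not change it. Day 1 meets the TEAE definition, so the AE is counted as treatment-emergent in the first part.

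**The case against.** The strongest case against is that the effect is very small. It needs an AE with no year, month or day of onset. The event is still counted as a TEAE and still appears in the individual listing. Section 8.7.1 counts a subject once per preferred term and once per system organ class within a part, so a moved event need not change any incidence. Safety is not tested and efficacy is unaffected. All of this stands, and it is why the point is minor.

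Much of the surrounding text is also blacked out: the sub-bullets of both partial-date rules, all the AE stop-date bullets, and the two treatment-group display formats in section 8.1. This limits what can be said. The legible stop-date heading covers only missing or partial stop dates, so a known stop date seems to lie outside it. Even so, the stop-date case has to be stated conditionally, and how switchers are labelled after the switch cannot be seen. The main point does not depend on these redactions, because the rule for a completely missing start date is legible and unconditional.

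A reader might infer three stronger things that the document does not support.

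- *Every undated AE first reported after the switch is misplaced.* Report date is not onset date. An AE that began on placebo and was first mentioned later is placed correctly.
- *The day-missing and year-only rules do the same around the switch.* Each has redacted sub-bullets that may refer to dose dates, so no rate can be attached.
- *A lower-dose tildrakizumab group is affected in the same way.* The dose of the switching tildrakizumab group is redacted. An event in that group would stay within tildrakizumab, so the shift towards placebo concerns placebo subjects only.

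**Conclusion.** The point holds and is minor. Under the legible rules, every completely undated AE in a placebo subject who later receives tildrakizumab is tabulated in the first part, under placebo. This is correct if onset came before the switch and wrong if it came after. The misattribution runs in one direction, which favours the study drug in the safety tables.

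Its size is unknown and probably small: 1 to 3 events under the assumed inputs above. It changes no efficacy result and no formal test. The conclusion rests on reading the first dose date as the first IMP dose and the first window as opening at that dose.

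The stop-date gap is a second, conditional part of the point: it exists unless redacted text closes it.

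**What to change.** Keep first-dose imputation for deciding whether an AE is treatment-emergent, and separate it from the allocation to part and treatment. Suggested additions to sections 7.2.2 and 8.7.1:

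- *For an AE with a completely missing start date, study part and treatment are assigned from other recorded information, namely the visit or part in which the AE was first recorded and any known stop date. The first dose date is used for this purpose only if these do not settle the part.*
- *Such events are flagged in the AE listing. A sensitivity tabulation assigns the unresolved events of subjects who switched to the post-switch tildrakizumab part.*
- *No imputed start date may be later than a known stop date. An AE with a known stop date before the first IMP dose is not a TEAE.*

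A known stop date before the switch settles the first part outright. First recording after the switch only makes the later part more likely. That is a reason to put the later-part default for unresolved events in a sensitivity tabulation and not in the main rule, where it would risk replacing one directional error with its opposite.

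The cost is SAP wording, one derivation step, a listing flag and a small extra table, all feasible before database lock. The derivation needs the database to hold the visit or date of first recording, which the SAP does not show and which should be confirmed. The downside is that a few events that began on placebo may be assigned to tildrakizumab.

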In addition, a listing containing individual subject adverse event data for TEAEs leading to discontinuation from study, Serious TEAEs, TEAEs leading to death, [REDACTED] will be provided separately. All AEs, including pre- and post-treatment AEs, will be presented in an individual subject data listing.

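### SAP 7.2.2 sets a completely missing AE start date to the first dose date even when the recorded stop date is earlier, so a resolved pre-treatment event would count as a TEAE

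*SAP*

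**What the plan says.** SAP section 7.2.2 has three rules for incomplete AE start dates.

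- Day missing: "If the start date has month and year but day is missing, the first day of the month will be imputed". Three redacted sub-bullets follow.
- Day and month missing: "If the start date has year, but day and month are missing, the 1st of January will be imputed". Again three redacted sub-bullets follow.
- Whole date missing: "If the start date of an event is completely missing, then it is imputed with the first dose date". This is a complete sentence with no sub-bullets, redacted or readable, beneath it.

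Four redacted bullets then deal with AE stop dates that are missing or partial. One readable check closes the AE rules: "After the imputation, the imputed dates will be compared against the date of death, if available". An imputed date later than death is replaced by the date of death.

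Section 8.7.1 uses the result. It states "Details for imputing missing or partial start dates of adverse events are described in", with the target of the reference blacked out, and it defines the analysis category: "TEAEs are defined as any AE occurring or worsening on or after the first dose of IMP". It then assigns TEAEs to study parts by event start date. On reporting it says "AE summary tables will be presented for TEAEs only and will include the following", and separately "All AEs, including pre- and post-treatment AEs, will be presented in an individual subject data listing".

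**The concern.** Setting an unknown start to the first dose date is a common, cautious convention when nothing else shows whether an event began before or after treatment. It stops being cautious when the record already answers that question. If the stop date is known and precedes first dose, the event cannot have begun on the first dose date. The rule then replaces an unknown value with one that contradicts a recorded value.

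What is at stake is whether the TEAE tables contain only events that could be treatment-emergent, and whether each event's dates are in a possible order. The SAP already accepts the principle that an imputed date must not pass a known later bound, because it applies that principle to the date of death. It does not visibly apply it to the event's own stop date.

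**Working it through.** The SAP gives no figure to reproduce on this point. The check is to put one record through the stated rules. The dates below are assumed for illustration.

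**Record:** first dose on day D; AE start completely missing; AE stop recorded as D − 5; subject alive.

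1. *Can such a record exist?* Yes. Section 8.7.1 provides for pre-treatment AEs in the subject listing, so events that ended before first dose are in the database.
2. *Start-date rule (7.2.2).* The whole date is missing, so start = D. The stop date plays no part in the readable rule.
3. *Stop-date rules (7.2.2).* They are introduced as covering missing or partial stop dates. The stop date here is complete, so they would not be expected to apply.
4. *Death check (7.2.2).* There is no date of death, so nothing changes.
5. *Date order.* Start = D and stop = D − 5. The start falls D − (D − 5) = 5 days after the stop, which is impossible.
6. *TEAE status (8.7.1).* An event starting on D starts on the day of first dose, and the definition includes that day. Read with the imputed start date, the event is a TEAE.
7. *Reporting (8.7.1).* As a TEAE, it enters the summary tables. As a pre-treatment event, it would have appeared only in the listing of all AEs.

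**General case.** For a recorded stop of D − k, the imputed start is k days after the stop. The contradiction arises for every k ≥ 1. At k = 0, start and stop are both D and the order is possible. The problem is therefore confined to stop dates strictly before first dose.

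**With an exception for such stop dates.** The record at D − 5 keeps its missing start date, is classed as not treatment-emergent, and stays in the all-AE listing. Records with a stop date that is missing, or is on or after D, are handled exactly as now.

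**The case against.** **Redaction.** A good deal of nearby text is blacked out: the sub-bullets of both partial start-date rules, all the AE stop-date bullets, the target of the cross-reference in 8.7.1, further lines of that section, and the table of derived variables in 7.1. A check of start against stop could be in any of these, and redacted text is not missing from the plan. This limits certainty but does not remove the point. The sentence at issue is fully readable and has nothing redacted beneath it, and the stop-date bullets are introduced for a different situation.

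**The TEAE definition may protect itself.** An event that ended before first dose neither occurred nor worsened after it, so on plain wording it is not a TEAE. That is a fair reading. However, 8.7.1 also points to the imputed start dates and places TEAEs in study parts by start date, so a programmer following the imputation rule would reach the opposite answer. The readable SAP does not say which prevails.

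**Little depends on it.** Section 8.7 plans no hypothesis tests on safety data, the error runs in the cautious direction, and events before exposure should fall on the randomized arms alike in expectation. All of this stands, and it is why the point is minor.

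**Stronger readings.** A reader might infer that the listings will show negative AE durations, but no readable text derives or lists an AE duration. A reader might also infer that the serious or discontinuation TEAE outputs are at particular risk. Nothing readable supports this for events that ended before any study drug was given.

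**Conclusion.** The point holds as a minor defect in a stated rule. Followed as written, 7.2.2 gives an impossible date order for an AE with no start date and a recorded stop before first dose. Applying 8.7.1 to the imputed date then counts that event as treatment-emergent.

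The effect is probably very small. It needs a completely missing start date, a recorded stop date, and a stop before first dose, all in the same record. The SAP gives nothing from which to derive how many such records there will be, so no count is offered. The direction is certain: these records can only add to the TEAE counts. Efficacy analyses are untouched.

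The conclusion assumes that no redacted passage compares the imputed start with the stop date, and that the imputed start date decides TEAE status. It says nothing about the two partial-date rules. A reader might extend the criticism to them, but their sub-bullets are redacted and may already deal with the stop date.

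**What to change.** Add an exception to the rule for completely missing start dates in 7.2.2, for example:

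> A completely missing AE start date is set to the date of first dose, unless the AE has a recorded stop date earlier than that. In that case the event is not treatment-emergent and its start date is left missing.

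The exception should use the recorded stop date, not an imputed one, and should not be extended to the partial-date rules. If a redacted passage already contains an equivalent check, a cross-reference to it from this rule is enough.

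The cost is one sentence in the SAP and a matching condition in the derivation of TEAE status. No other record changes, and affected events remain visible in the listing of all AEs. If the SAP can no longer be amended, the same handling can be described and justified in the CSR, as section 1 of the SAP provides for deviations.

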8 STATISTICAL METHODS

8.1 General Statistical Conventions

All statistical procedures will be completed using SAS version 9.4 or higher.

Unless otherwise stated, all statistical testing will be two-sided and will be performed using a significance (alpha) level of 0.05.

Continuous variables will be summarized using descriptive statistics, including number of subjects (n), mean, median, standard deviation (SD), minimum and maximum. One additional decimal point for mean and median and [REDACTED] for SD will be used.

For categorical variables, summaries will include counts of subjects and percentages. [REDACTED]

For summary purposes, baseline will be defined as the last available value prior to the date of first IMP administration; all summaries will be presented by treatment group, unless otherwise specified.

For reporting purpose, summary tables for efficacy variables and safety variables will be displayed by nominal visit as appropriate. Unscheduled assessments will not be included in the summary tables, but will be in data listings.

All subject data, including those derived, will be presented in individual subject data listings. Unless otherwise stated, unscheduled visit results will be included in date/time chronological order, within patient listings only. All listings will be sorted by treatment group, subject number, date/time and visit. The treatment group as well as patient's sex and age will be stated on each listing. Unless otherwise stated, data listings will be based on all randomized subjects.

The treatment groups will be displayed in the format below in tables including [REDACTED]:

- [REDACTED]
- [REDACTED]
- [REDACTED]
- [REDACTED]
- [REDACTED]

The treatment groups will be displayed in the format below for tables including [REDACTED] and all listings:

Statistical Analysis Plan (SAP)

- [REDACTED]
- [REDACTED]
- [REDACTED]
- [REDACTED]
- [REDACTED]

8.2 Protocol deviations

Population membership details will be listed, including reason for exclusion from each population.

All major protocol deviations identified will be summarized by treatment group and overall.

A listing will include the inclusion/exclusion criteria violated at Screening and at Baseline Visits as well as other protocol deviations identified based on data recorded on the eCRF and/or protocol deviation Logs [REDACTED]

